For HIC Use Only**Date Approved****Human Investigation Committee Signature****This protocol is valid through** _____**SECTION V: RESEARCH PLAN**

1. **Statement of Purpose:** State the scientific aim(s) of the study, or the hypotheses to be tested. Well-controlled randomized clinical trials of computer-assisted therapies are very rare, and there are few that would meet current methodological standards established for traditional evidence-based treatments. We propose to conduct a randomized clinical trial of our web-based version of Computer Based Training in Cognitive Behavioral Therapy (CBT4CBT) to evaluate its effectiveness relative to therapist-delivered cognitive behavioral therapy or standard outpatient counseling with participants with alcohol use disorder. Specific aims are as follows:

Aim 1 – Evaluate the efficacy of CBT4CBT and clinician-delivered CBT relative to standard treatment for reducing alcohol use through an 8-week randomized trial with 6-month follow-up. Our primary hypothesis is that either form of CBT will be more effective than standard treatment at increasing the percentage of days abstinent (PDA)^{2, 3} during treatment (8 weeks) and through the follow-up (6 months), assessed via Timeline FollowBack interviews^{4, 5}. Secondary outcomes will include percentage of heavy drinking days (PHDD)^{6, 7}, urine ethyl glucoronide analysis (EtG)⁸⁻¹⁰, drinking-related consequences^{11, 12}, quality of life¹³, and cost effectiveness¹⁴.

Aim 2 – Evaluate the extent to which CBT's putative mechanisms act as mediator of treatment effect on reducing alcohol use in both forms of CBT relative to standard treatment.

Hypothesized mechanisms include enhanced behavioral, cognitive, and affective control, measured within treatment by indices reflecting acquisition and implementation of targeted skills (behavioral role-play assessment¹⁵, coping strategies inventory^{16, 17}, and measures of homework completion and knowledge of CBT). Latent growth curve modeling will test for mediation using the product of coefficients method^{18, 19}. We hypothesize:

- (a) greater increases in skills acquisition for those assigned to either form of CBT compared to TAU;
- (b) increased acquisition of skills during treatment will be associated with greater PDA during follow-up;
- (c) CBT's effect (in either delivery format) on PDA will be mediated by skills acquisition.

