C.1.b. Coping skills acquisition as a mediator of treatment outcome in CBT4CBT

Evidence for the promise of using a computer-based CBT for evaluating mechanisms comes

from [name] analysis of differential acquisition of coping skills in the initial CBT4CBT trial⁹⁶. We used a role-playing exercise we have validated in previous research (Drug Risk Response Test, DRRT)¹⁵ and adapted to assess the specific coping skills taught in the CBT4CBT modules. Based on independent ratings (i.e., raters blind to treatment condition and time point) of pre/post-treatment/follow-up comparisons from 52 participants, there were significant group by time interactions, **indicating those assigned to CBT4CBT had a significantly greater increase in the quality of their coping responses across the entire study period ($F=9.3, p=.004$;**

Figure 1. Data from this trial also suggest that acquisition of skills during treatment may be a mediator of substance use outcomes (Fig 2, below). A series of regression equations

[figure not shown]

Figure 2 Quality of coping skills as mediator of CBT4CBT

Figure 2 is a path diagram showing the relationships between treatment condition (CBT vs TAU), quality of coping skills, and consecutive days abstinent. The paths are as follows:

- CBT vs TAU to Quality of Coping Skills: (2) $a = 0.26^*$
- CBT vs TAU to Consecutive days abstinent: (1) $c = 0.65^*$, (4) $c' = -1.54$
- Quality of Coping Skills to Consecutive days abstinent: (3) $b = 9.19^{**}$

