The text continues to describe the results of these paths, demonstrating a significant effect of treatment condition on the quality of coping responses ($a = .26, se=.11, p<.05$) favoring CBT4CBT (TAU = 3.89, CBT4CBT = 4.40; $F=4.6, (df 1,40), p <.05$), and a significant effect of the mediator (quality of coping responses) on outcome, controlling for treatment condition ($b = 9.19, se=3.24, p<.01$). Using the product of coefficients method^{18, 19} to determine if the mediated effect is significantly different from zero, calculated as $[(a \times b)/(se_a \times se_b)]$, resulted in $Z=6.64, p<.05$. Also, confidence limits for the mediated effect using the program PRODCLIN¹⁵¹ resulted in upper and lower confidence intervals of 5.39 and 0.31, consistent with a statistically significant mediated effect. This suggests improvement in the quality of skills acquired during treatment was a mediator of post-treatment drug use. **This comparatively strong evidence supporting skills acquisition as a potential mediator of outcome in CBT4CBT is striking,**

[figure not shown]
given that empirical support for mediation in CBT in the addictions has been elusive^{59, 68, 124}.

C.1.c. Cognitive factors associated with effectiveness of CBT4CBT

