Adequacy of sample size: *H1a* – Using conventional effect size estimates, we determined that our proposed sample size of 60 per condition would be sufficient for detecting a small-medium effect ($d=.35$) of treatment on PDA using a random effects regression model (2 groups, PDA by month, 3 data points, ICC=.6, alpha=.05, beta=.80). *H1b* – The proposed sample is sufficient to detect a medium effect ($d=.50$) through the follow-up period with a random effect regression model (2 groups, PDA by month, 7 data points, ICC=.6, alpha=.05, beta=.80). These effect sizes are conservative, based on estimates from completed studies of CBT4CBT^{119, 122}.

Power calculations	Power	Estimated effect size	# of datapoints	Sample size per cell
H1a: (Clinician CBT + CBT4CBT stand-alone) v TAU, main effect for active treatment	.80	.35	3	60
H1b : (Clinician CBT + CBT4CBT stand-alone) v TAU, main effect for follow up	.80	.50	7	60

Aim 2 – Evaluation of skills acquisition as mediator of CBT effects:

Latent growth curve modeling will be the principal strategy for evaluating mediation using Mplus version 7²⁵¹. The product of coefficients method^{18, 19} will be used to determine the mediating effects of skills acquisition during the treatment period on PDA during follow-up. We will be using the 6-month period following treatment as our alcohol use outcome in this model to support the temporal relation criterion⁶⁴, as well as to evaluate the delayed emergence of CBT's effect on alcohol use¹³⁹. This model will test:

- **H2a:** *Effect of CBT on acquisition of skills (a₂ path: X→M):* Clinician-CBT>TAU; CBT4CBT>TAU
- **H2b:** *Effect of change in acquisition of skills on PDA by month during follow-up (b₂ path: M→Y)*

- **H2c:** *Indirect effect of CBT on PDA via change in acquisition of skills ($a_2 * b_2 / se_{a2} * se_{b2}$)*

Adequacy of sample size: Parameter estimates from our initial trial of CBT4CBT that supported coping skills acquisition as a mediator of treatment effects on substance use⁹⁶ were used to estimate effect sizes of treatment condition on PDA via skills acquisition ($a=.26$; $b=.59$). Based on these effect sizes and power estimates for testing mediation derived from a simulation study⁹⁴, we will have adequate power (.80) to detect significant mediating effects with the proposed sample size of 60 per condition.

SECTION VI: RESEARCH INVOLVING DRUGS, BIOLOGICS, RADIOTRACERS, PLACEBOS AND DEVICES

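### The H2c mediation statistic multiplies two z-values; read as a Z, it would often declare mediation when CBT does not change skills

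*Combined protocol and SAP*

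**What the plan says.** The Statement of Purpose (Section V, item 1, Aim 2) says "Latent growth curve modeling will test for mediation using the product of coefficients method", and hypothesis (c) is that the effect of CBT "on PDA will be mediated by skills acquisition". Section V, item 11, Aim 2 repeats that the product of coefficients method "will be used to determine the mediating effects of skills acquisition during the treatment period on PDA during follow-up". Both C.2.f and item 11 then define H2c as "Indirect effect of CBT on PDA via change in acquisition of skills ($a_2 * b_2 / se_{a2} * se_{b2".

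In that line the denominator has no brackets. C.1.b shows the intended form: in the initial CBT4CBT trial the method was used "to determine if the mediated effect is significantly different from zero, calculated as $[(a \times b)/(se_a \times se_b)]$, resulted in $Z=6.64, p<.05". The same paragraph also reports PRODCLIN confidence limits of 0.31 and 5.39. C.1.c reports a second mediation Z, of 8.55, again alongside a confidence interval.

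The Aim 2 text for this trial gives no critical value, reference distribution or interval for H2c. It lists H2a, H2b and H2c as separate tests and does not make H2c depend on the other two.

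**The concern.** Dividing a × b by se(a) × se(b) gives (a/se(a)) × (b/se(b)), which is the product of the two path z-values. Its spread depends on how strong the paths are. If a is zero but b is not, the statistic behaves like a null z multiplied by a number near the b-path z, so it grows as skills predict drinking more strongly, even though nothing is mediated. No single cut-off can control that.

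This is the case the mediation test has to rule out: skills predict later abstinence, but CBT does not raise skills more than TAU. A false positive would support hypothesis (c), the mechanism claim of Aim 2.

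**Working it through.** **1. Reproduce the plan's own figure.** C.1.b gives a = .26 with se .11, and for the other path "b = 9.19, se=3.24, p<.01".

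- a-path z = .26/.11 = 2.36
- b-path z = 9.19/3.24 = 2.84
- product = (.26 × 9.19)/(.11 × 3.24) = 6.70

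The printed value is 6.64. Rounding of the four inputs allows 6.28 to 7.17, so the printed Z is the product of the two z-values.

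**2. Compare with valid summaries of the same data.**

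- First-order (Sobel) z = product / √(2.36² + 2.84²) = 6.70/3.69 = 1.82, p = .07.
- Distribution-of-product 95% interval (4 million draws): 0.24 to 5.50, close to the printed PRODCLIN limits of 0.31 to 5.39.

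The interval excludes zero, so the conclusion of that trial is not in dispute. The figure of 6.64 is still not a Z.

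**3. Show the problem by hand.** 1.40 × 1.40 = 1.96. Two paths with p = .16 each would be read as significant mediation.

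**4. Expected b-path z in this trial.** The documents do not give it, so the error is shown over a range of values μ:

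- 2.84, the initial trial's own value.
- 4.3 to 4.8, that value scaled to 120 participants (one CBT arm against TAU, 60 each): 2.84 × √(120/52) = 4.31, using "comparisons from 52 participants"; or 2.84 × √(120/42) = 4.79, using n = 42 from the degrees of freedom in "CBT4CBT = 4.40; $F=4.6, (df 1,40), p <.05".
- 6.4 to 7.9, if the planning value b = .59 is in SD units: .59 × √117 = 6.38 with residual SD 1, or 6.38/√(1 − .59²) = 7.90 if fully standardised.

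**5. Error rate with a = 0.** Take the a-path z as N(0,1) and the b-path z as N(μ,1), independent. For cut-off c the rate is the integral over t of φ(t − μ) × 2[1 − Φ(c/|t|)]. The joint rule (H2a and H2b both significant) has rate .05 × P(|b-path z| > 1.96). Entries are percentages of trials.

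| μ | H2c beyond 1.96, two-sided | of which favouring CBT | H2c beyond 2.18, two-sided | H2c beyond 1.96 while H2a is not significant | joint rule |
|---|---|---|---|---|---|
| 0 | 6.5 | 3.2 | 5.0 | 4.5 | 0.3 |
| 1.00 | 13.6 | 6.8 | 11.2 | 10.6 | 0.9 |
| 1.96 | 29.8 | 14.9 | 25.9 | 25.5 | 2.5 |
| 2.84 | 45.3 | 22.7 | 41.0 | 40.5 | 4.1 |
| 4.3 | 63.1 | 31.5 | 59.4 | 58.1 | 5.0 |
| 4.8 | 67.0 | 33.5 | 63.6 | 62.0 | 5.0 |
| 6.4 | 75.4 | 37.7 | 72.7 | 70.4 | 5.0 |
| 7.9 | 80.1 | 40.0 | 77.9 | 75.1 | 5.0 |

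The 2.18 cut-off is the .05 critical value for a product of two null z-values. It is correct only in the first row.

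**6. Checks.** Simulated regressions (60 v 60, no direct effect, complete data, 40,000 replicates) with a = 0 and b = .59 gave 75.6% with residual SD 1 and 80.2% with total variance 1; the joint rule gave 5.0% in both. With a = b = 0 the product gave 6.6–6.8%. The distribution-of-product interval with a = 0 had error of 0.2% at μ = 0, 3.6% at 2.84, 4.5–4.7% at 4.3–4.8 and 5.5% at 6.4–7.9.

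**The case against.** The strongest reply is that the plan never says H2c will be read alone against 1.96. H2a, H2b and H2c are introduced together as what one model tests. Section A2 endorses a four-criterion causal chain and faults earlier evidence for not meeting all of it, so claiming mediation with a null H2a would go against the team's own framework. Both earlier uses of the Z came with confidence limits. The stated power also points away from the product rule: with a = .26, b = .59, a standardised treatment variable and N = 120, the joint rule has simulated power of .80, whereas the product against 1.96 has .99. With 0/1 coding the figures are .30 and .91, so .80 does not match the product rule under either coding.

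Much of this is fair. The cut-off is an inference, drawn from the way C.1.b attaches p<.05 to the same ratio. A careful reader would see a clash with a null H2a. The range is wide, the scale of .59 is not given, and 2.84 comes from a drug-use trial with a different outcome. Hypothesis (c) is directional, so the rates of false support for CBT are half the two-sided ones.

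It does not remove the problem. The plan prints an invalid statistic as the test of H2c, while the interval and the joint requirement that would make the claim safe are not carried into Aim 2. The other plausible cut-off, 2.18, helps little.

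**Conclusion.** The concern holds. The printed H2c statistic is a product of two z-values and does not test the indirect effect. At a b-path z of 2.84 with no effect of CBT on skills, it would indicate mediation in about 45% of trials, 23% in favour of CBT. The two-sided rate is 63–67% if that z scales to 120 participants, and 75–80% if b = .59 is in SD units. If the b path is weak the excess is small: 6.5% at zero and 14% at a z of 1.00.

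These rates assume H2c is read alone against 1.96, one observed mediator in place of the latent intercept and slope, and complete data. The growth model would change the b-path z but not the algebra, so the table can be entered at whatever value applies. No claim is made about the stated .80 power or the sample size. Aim 1, H2a, H2b and the conclusion of the initial trial are unaffected. It should be fixed because it can reverse the answer to hypothesis (c).

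**What to change.** In C.2.f and in Section V, item 11, replace the H2c formula with wording such as:

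> H2c: the indirect effect a2 × b2, estimated in the Mplus growth model, with a 95% confidence interval from the distribution of the product (PRODCLIN) or the bootstrap. Mediation is claimed only if the interval excludes 0.

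Choose one of the two interval methods in advance. PRODCLIN was already used for the result in C.1.b. The cost is one line of text in two places and one additional output; data collection, the mediator measures and Aim 1 do not change. The drawback is that mediation will be declared less often than with the printed statistic.
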